#### Lipidomic analysis in PCOS:

Sun et al first reported changes in plasma lipid profile of PCOS patients using NMR in 2012(2). 34 PCOS (average age 26.9) and 36 controls (average age 27.2) were analyzed in the cross sectional study. Decrease in glycerophosphocholine/choline was observed in the PCOS patients. However, since NMR was, identity of these lipids remained elusive to the study. In 2015, Houla et al (7) reported use of LC-MS, which is much more informative on the identity of lipids, to analyze lipidomic changes plasma samples of PCOS patients. In the cross sectional study involving women aged 18-40 years, 40 PCOS and 40 non-PCOS controls were recruited. Significant changes in phospholipids, sphingomyelins, diand tri- acylglycerols were observed. However, the average BMI of PCOS patients (29.5) were significantly higher than that of controls (25.4), which calls for a more guarded approach in associating changes in lipid composition to PCOS alone. Moran, L et al (8) examined correlation between features of PCOS and lipidomic changes in a cross-sectional study involving women with (n = 64) or without PCOS (n = 92) aged 18-45. The changes in lipid composition correlated most with central obesity and free androgen index. But even in this study both body weight and BMI of PCOS patients were significantly higher than control. Li S et al (9) reported analysis of the changes in lipids including polyunsaturated fatty acid metabolites in 32 newly diagnosed PCOS patients compared to 34 non-PCOS subjects. Results indicated an opposing effect of insulin and androgen on bioactive metabolites. However, the BMI of the control obese and obese PCOS subjects were significantly different in this study. In 2018, Jove M et al (10) reported analysis of plasma lipidome of 20 lean healthy controls and 14 PCOS patients. Significant downregulation of glycerophospholipids, glycerolipids and sphingolipids were observed suggesting a widespread alteration in lipid metabolism which might influence cellular signalling in PCOS patients.

While these studies indicated changes in lipid metabolism associated with PCOS, several of them failed to account for confounding factors such as difference in BMI and/or age. In addition, all of these studies were single-time point cross-sectional in nature. Therefore, they do not yield any information on evolution lipidomic signature during pathogenesis. Longitudinal nested case-control study is essential not only to identify any early signature for risk prediction or diagnosis but also to hypothesize on and investigate into the causal relationship between derangement of lipid metabolism and PCOS. It should be noted that neither any longitudinal nor any cross-sectional sectional lipidomic analysis has ever been reported in Indian PCOS patients.

#### 1.1.3 Reasons for taking up the project.

PCOS has been shown to affect up to one in every five women worldwide. However, there is a paucity of epidemiological data and it is suspected to be underreported in India. More importantly, due to the social stigma associated with some of the consequences, often it is diagnosed late or not reported. This eventually adversely affects not only metabolic and cardiovascular health but also psychological health of the patient. Therefore, identification of signatures that can be used as an early warning system is highly warranted for timely intervention to effectively manage the condition. Such signatures may be useful for large- scale screening of vulnerable subjects. However, there has been a dearth of efforts to that end worldwide. Existing literature indicates to involvement of derangement of lipid metabolism in PCOS. A longitudinal study with nested case-control design on analysis of evolution of lipidomic signature can yield such signatures. Elucidation of molecular events associated with such early signatures of PCOS onset may also lead to identification of putative targets for novel therapeutic intervention.

1.1.4 Relevance to state priorities and fulfilment of socio-economic objectives of the Government.

Women empowerment has been one of the top priorities of the state. Improvement of women's physical and psychological health is an essential component of this endeavour. Identification of signatures for risk prediction and early detection of PCOS would help in effective management of the condition. This would not only help to increase the physical and mental productivity of women but also significantly reduce the financial burden for healthcare

- 1.1.5 Financial resources committed by the applicant/ host Institution: None
- 1.1.6 Whether this project or similar project(s) have been taken elsewhere in the State/ Country.
- 1.1.7 Please provide links of previous such work /research taken place.
- 1.1.8 How this present work is unique from the others such work done in this area so far
- 1.1.9 Novelty of the idea [Explain how your idea is innovative and how it is differentfrom the existing idea/ products/ processes in your area of interest]
- 1.1.10 Please provide necessary inputs on the list of patents that appear to cover any part of the project/ technology, if any. If so, please mention patent number, patent title and patent assignee.
- 1.1.11 Number of research paper/article expected to be published in any journal inconnection to this project? (If yes, furnish details)
- 1.1.12 Number of book(s)/chapter(s) expected to be published in any journal in connection to this project? (If yes, furnish details. Workshops, Seminars etc. not to be counted or listed)
- 1.1.13 Number of outreach programme expected be done to disseminate the probable outcome of this project?
- 1.1.14 Number of seminar/symposium/conference expected to be attended in connection with this project at State, National or International?

#### **1.2** Hypothesis and aims and objectives (up to one page):

This proposal aims to longitudinally monitor a population of young adult women in nested casecontrol study design to identify changes in serum lipidome that can act as early marker for PCOS onset. Specific aims of the project are as follows:

1)Thorough physio-clinical evaluation including analysis of true adiposity, serum biochemistry, ovarian morphology and liver steatosis and fibrosis.

2)Characterization of differences in serum lipidome of PCOS and naive subjects.

3)Characterization of evolution of lipidomic signature during onset of PCOS in naive subjects.

#### **1.3** Significance of the project (up to one page):

This project will involve application of modern tools for thorough analysis of patient physiology and status of PCOS. It will also involve application of cutting edge chromatography and mass spectrometry platforms for detailed characterization of lipidome. Success of the project will be of immediate help to clinicians and patients in terms of screening and diagnosis of PCOS. In addition, the results may also yield clues to identify novel therapeutic targets for PCOS.

#### **1.4** Research design, methodology, timelines and milestones (up to ten pages):

#### Study Design:

Longitudinal nested case-control, hospital-based.

#### **Study settings**

OPD of Department of Endocrinology and Metabolism IPGME&R and SSKM hospital.

#### **Study population**

Freshers admitted in MBBS course at IPGME&R and SSKM hospital. We aim to recruit 200 subjects.

#### Sampling methods

All voluntarily consenting adults will be enrolled and clinically evaluated as per Rotterdam criteria to designate them as

PCOS or non-PCOS cases.

#### **Inclusion criteria**

[figure not shown]
All voluntarily consenting freshers with age > 18.

#### **Exclusion criteria**

Lack of consent to undergo longitudinal monitoring, presence of any chronic infection, type I diabetes, eating disorder, ongoing medication connected to lipid metabolism (such as statins), addiction to tobacco or alcohol and any life- threatening condition. Untreated Hypothyroid, Hyperprolactemia, NCCAH.

#### **Overview of the Workflow:**

Approximately 200 young adult subjects will be enrolled and examined for PCOS incidence as per Rotterdam criteria in addition to comprehensive physio-clinical, radiological and biochemical evaluation. This exercise will be repeated for all subjects every year.

**Figure 1:** Schematic representation of overall plan of work for identification of early markers of PCOS using serum lipidomics.

Serum samples collected during this exercise will be subjected to lipidomic analysis using Ultra-performance liquid chromatography (UPLC)-electrospray ionization mass spectrometry (ESI-MS) as well as gas chromatography coupled with mass spectrometry (GC-MS). These data will be combined and mined using multivariate statistical analysis to identify features of interest. This will be further subjected to rigorous statistical analysis for robustness of association of signatures with PCOS.

#### **Study Techniques:**

#### **Clinical assessment:**

Subjects will be assessed to record body weight, BMI, waist circumference (WC), WHR, , blood pressure, body fat, hepatic steatosis and fibrosis by Fibroscan analysis. Any family history of PCOS and information on ongoing medication or medication within 1 month preceding clinical assessment will be recorded. Diagnosis of PCOS will be based on Rotterdam Criteria, i.e., presence of any two of the following features: hyperandrogenism (hirsutisim, acne, alopecia), ovulatory dysfunction (oligo-ovulation, anovulation) and PCOM (by USG) while excluding presence of thyroid dysfunction, hyperprolactinemia, Cushing's syndrome, and virilizing tumors.

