#### Definition, Criteria for Diagnosis and Their Limitations:

PCOS may present with a number of clinical manifestations such as clinical hyperandrogenism (hirsutism), acne, alopaecia, biochemical hyperandrogenemia (elevated levels of testosterone and dihydroxyepiandrostenedione sulfate), oligomenorrhea, amenorrhea, anolvulation and polycystic ovarian morphology (PCOM) (1-3). In addition, PCOS has also been found to be associated with obesity, insulin resistance and hyperinsulinemia, elevated cholesterol and triglycerides, sleep apnea, depression and

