anxiety (1, 2, 4). Patients may present with only a few of them. Widespread heterogeneity is observed in the types of symptoms presented by PCOS patients. Consequently, there are three existing definitions for PCOS. According to 1990 NIH-National Institute of Child Health and Human Development Conference of PCOS recommendations, major criteria for PCOS should include (in order of importance): hyperandrogenism and/or hyperandrogenemia, oligo-ovulation and the exclusion of other known disorders such as thyroid dysfunction, hyperprolactinemia, Cushing's syndrome, and virilizing tumors (5). In 2003, European Society of Human Reproduction and Embryology and the American Society of Reproductive Medicine jointly proposed (6, 7) diagnosis of PCOS to satisfy any two of the following: hyperandrogenism, ovulatory dysfunction and PCOM. In 2006, Androgen Excess and PCOS Society (AE–PCOS) Position Statement (8) mandated requirement of the presence of hyperandrogenism, which must be accompanied by evidence of ovarian dysfunction in the form of ovulatory dysfunction and/or PCOM. Although the broader 2003 recommendation, called Rotterdam criteria (6,7) is most widely accepted, all three definitions are valid at present. This often leads to significant variation in PCOS incidence in epidemiological studies. Most importantly, the narrower definitions may exclude PCOS patients that do not present clinical hyperandrogenism. Androgen excess is often considered essential component of PCOS. Although often considered an essential component of PCOS, only 80-85% of women with clinical hyperandrogenism develop PCOS (9). This indicates contribution of other factors to pathogenesis. Detection of polycystic ovarian morphology (PCOM) by USG is also found to be inadequate to predict PCOS since a PCOS patient may be yet to develop PCOM while almost 20-30% women present polycystic ovary (10, 11). Although hirsutism serves as a very important feature, white and black women often tend to grow facial hair while, some patients, particularly, those of East Asian ethnicity may not manifest it (1, 12). Measurement of serum androgen levels also yield important clues in diagnosis. However, only 50-75% women with PCOS has been found to have elevated levels of testosterone and dehydroepiandrosterone sulfate(DHEAS) (13).

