#### Lipid Metabolism and PCOS:

Hyperandrogenemia is one of the defining biochemical features of PCOS. Androgens such as testosterone and DHEAS, which are used as a measure of hyperandrogenism, are synthesized from DHEA. Cholesterol is converted by P450scc to pregnonelone, which is further converted to DHEA by P450c17. Cholesterol biosynthesis involves mevalonate pathway starting from acetyl CoA. It is interesting to note that *de novo* lipid biosynthesis also starts from acetyl CoA. Lipid metabolism through beta-oxidation, in turn, ends at acetyl CoA, which can then enter TCA cycle to produce energy. So, androgen and cholesterol biosynthesis shares common biochemical intermediate of lipid metabolism. Androgens have also shown to activate de novo lipogenesis through SREBP1 in prostate cancer cells (1, 2). Interestingly, hyperandrogenemia was found to be associated with dyslipidemia in obese women irrespective of PCOS status (3).

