#### **Biochemical Profiling:**

A part of the serum samples will be used to analyze hepatokine, cytokine, adiponectin, leptin, HbA1c, androgen (testosterone and DHEAS) levels along with LFT, CRP, Insulin, HOMA-IR, fasting glucose and lipid profile.

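### The PCOS case definition counts only clinical signs as hyperandrogenism, although the protocol treats serum androgens as a measure of it and already assays them, so some biochemical cases can be labelled naive

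*Protocol*

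**What the plan says.** The operative rule is in the protocol's Clinical assessment section: "Diagnosis of PCOS will be based on Rotterdam Criteria, i.e., presence of any two of the following features". The list that follows reads "hyperandrogenism (hirsutisim, acne, alopecia), ovulatory dysfunction (oligo-ovulation, anovulation) and PCOM (by USG". Three clinical signs stand for hyperandrogenism, and no serum measure is named.

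Other sections treat hyperandrogenism more broadly:

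- Definition, Criteria for Diagnosis and Their Limitations names "biochemical hyperandrogenemia (elevated levels of testosterone and dihydroxyepiandrostenedione sulfate" as a manifestation separate from hirsutism, acne and alopecia. Its account of the Rotterdam criteria does not restrict hyperandrogenism to clinical signs, and it faults narrower definitions for missing patients who lack them. It also reports that "only 50-75% women with PCOS has been found to have elevated levels of testosterone" and DHEAS.
- Lipid Metabolism and PCOS states "Hyperandrogenemia is one of the defining biochemical features of PCOS" and continues "Androgens such as testosterone and DHEAS, which are used as a measure of hyperandrogenism".
- Biochemical Profiling includes "androgen (testosterone and DHEAS) levels along with LFT, CRP, Insulin, HOMA-IR" in the serum panel. The evaluation is repeated yearly.

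The Data mining section divides subjects into those with PCOS at the start, those who develop it during the study, and those who never do. Case status also underlies set A (cases against controls at a time point), set B (paired change with onset in naive subjects), the ROC analyses and the prediction of later PCOS from baseline serum.

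**The concern.** The study looks for lipid changes that precede PCOS, so everything depends on who is PCOS-free at entry and when each woman becomes a case. If the definition omits a feature that the protocol itself regards as part of the disease, some women who already have it enter as naive. There are two possible consequences.

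- A woman who never gains a further feature stays among the non-PCOS controls, which would tend to blur the differences that set A seeks.
- A woman who later gains a clinical sign or the other ovarian feature is counted as a new onset. Her paired change in set B then reflects an added feature, not onset. In the baseline ROC analysis her first serum sample is treated as pre-disease, so detection of existing disease could pass for prediction.

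The second consequence bears directly on the study's aim. A few such women could carry weight if the converter group is small.

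**Working it through.** The protocol derives no sample size, power or event figure on this point, so there is nothing to reproduce. The check has two parts.

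**1. Which women change status.** Let C = clinical sign, B = raised serum androgens, O = ovulatory dysfunction, P = polycystic ovarian morphology, each 0 or 1.

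- Rule as written: PCOS if C + O + P ≥ 2.
- Rule with serum androgens counted: PCOS if max(C, B) + O + P ≥ 2.

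The rules can differ only when C = 0 and B = 1. They then become O + P ≥ 2 and O + P ≥ 1, which disagree only when O + P = 1. So 2 of the 16 patterns change, from non-PCOS to PCOS:

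- raised androgens, no clinical sign, ovulatory dysfunction only;
- raised androgens, no clinical sign, polycystic morphology only.

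Women with both ovarian features are cases under either rule. Women with neither are non-cases under either rule.

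**2. How many women (illustration only).** From the documents: 200 subjects (Study population), and prevalences of 6% and 22.5% from two Rotterdam-based studies of young women in Table 1 of Epidemiology. Other Rotterdam rows there run as high as 50%. Three inputs are not in the documents and are assumed: f, the share of cases with one of the two patterns; g, the share of those who later gain a further feature; and the two-year incidence of true onset.

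- Baseline cases: 200 × 0.06 = 12; 200 × 0.225 = 45.
- Labelled non-PCOS with f = 5% to 30%: 12 × 0.05 = 0.6 to 12 × 0.30 = 3.6; and 45 × 0.05 = 2.25 to 45 × 0.30 = 13.5.
- False onsets = missed × g. The remaining missed × (1 − g) women stay among the controls.
- Share of apparent onsets that are false = false / (false + true onsets).

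With f = 10% and 5% two-year incidence:

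| Prevalence | Missed | True onsets | g = 0 | g = 25% | g = 50% | g = 100% |
|---|---|---|---|---|---|---|
| 6% | 12 × 0.10 = 1.2 | 188 × 0.05 = 9.4 | 0% | 0.3/9.7 = 3% | 0.6/10.0 = 6% | 1.2/10.6 = 11% |
| 22.5% | 45 × 0.10 = 4.5 | 155 × 0.05 = 7.75 | 0% | 1.125/8.875 = 13% | 2.25/10.0 = 22.5% | 4.5/12.25 = 37% |

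Across a wider grid (f 5% to 30%, incidence 2% to 10%, g 0 to 100%) the share runs from 0% to 81%. The top value is 13.5 / (13.5 + 3.1), at 22.5% prevalence, f = 30%, 2% incidence and g = 100%. That spread shows that the assumptions fix the answer and the documents do not.

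The 50-75% figure for raised androgens does not supply f. It includes women who also have a clinical sign or both ovarian features, and they are cases under either rule.

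**The case against.** The strongest reply is that the bracketed signs are only examples. Sampling methods and Overview of the Workflow assign status by the Rotterdam criteria, which the background describes without a limit to clinical signs. The background also says that serum androgens help in diagnosis, and the baseline row of the work plan lists assays and diagnosis together. On this reading, raised androgens already count.

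Part of this stands: the text does not prove that biochemical cases will be excluded in practice. It does not remove the conflict. The diagnostic sentence presents its list as what the criteria mean, and the only signs it gives for hyperandrogenism are clinical. Overview of the Workflow places biochemistry alongside the Rotterdam examination, not within it. The work-plan rows for months 13-15 and 25-27 list assays without diagnosis. At best, two readings are open, and they could be applied differently at baseline and follow-up.

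A missing cut-off is not the complaint, since an analysis plan that is not shown could supply one.

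A reader might infer that every woman with biochemical hyperandrogenism will enter as naive and become a false onset, or that false onsets could be as numerous as real ones. The documents support neither. Only two patterns are affected, a false onset requires a further feature to appear later, and parity depends on values of f, g and incidence that the protocol does not give.

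**Conclusion.** The point holds in a limited form. As written, the case definition conflicts with the protocol's own account of hyperandrogenism. It can place women with raised androgens, no clinical sign and exactly one ovarian feature among the naive subjects, where they become either contaminated controls or, conditionally, false onsets. This is a stated rule in conflict with other sections, not a detail left for later.

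The classification result (2 of 16 patterns) needs no assumption beyond reading the list literally. The number of women cannot be derived, so the ranges above are illustrations and should not be cited as estimates. The matter should be corrected because case status drives every comparison and the correction is cheap. Nothing here shows that the study's results would be invalid.

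**What to change.** - Reconcile Clinical assessment with Definition, Criteria for Diagnosis and Their Limitations, Lipid Metabolism and PCOS, and Biochemical Profiling. The research case definition should state whether the serum androgens already measured count as hyperandrogenism. That choice belongs to the investigators.
- If they count, the investigators set the laboratory limit in advance. Whichever definition is chosen is applied identically at all three visits.
- Define naive by that same definition.
- Run the alternative definition (with or without serum androgens) as a sensitivity analysis of case status, and report how many women change group.
- If serum androgens count, report androgens measured by GC-MS apart from the candidate lipids, because they would otherwise help to predict a label that they partly define.

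Cost: a few sentences, an agreed laboratory limit if androgens count, and a second run of the planned analyses. The assays are already planned. The small downside, if androgens count, is that the GC-MS androgens leave the candidate list.

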#### Sample collection:

Serum will be used for lipidomic analysis since an earlier analysis revealed that although most of the lipids were present at similar levels in both plasma and serum, serum showed higher level of oxidative lipid metabolites. Serum samples will be collected from subjects fasting overnight. 0.5 ml serum will be divided into  $100\mu$ L aliquots in 2 ml screw-cap tubes and stored at -80°C until further analysis. Rest of the serum sample will be sent immediately for biochemical assays mentioned below. 1 ml serum Stored at -80°C in  $100\mu$ L aliquots in 2 ml screw-cap tubes until further analysis.

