(B) GC-MS Analysis: Lipid extract will be mixed with internal standards for derivatization and extraction. Methyl esters of fatty acids will be prepared via esterification using Methanolic HCl. Methyl esters will be extracted using hexane, evaporated to dryness under nitrogen and reconstituted in hexane containing internal standard for GC-MS quality control. For steroids, samples will be derivatized using MSTFA containing 0.5% TMSI. Compounds will be separated on a HP5-MS or DB5 column with helium as the carrier gas in gas chromatograph (Agilent 7890B) and ionized through electron impact ionization and analyzed using a single quad mass spectrometer (Agilent 5977B). Total ion chromatogram will be aligned and deconvoluted to extract features and identify changes in composition. Identification of compounds of interest will be through analysis of fragmentation pattern, matching against NIST Library and comparison with authentic standards (whenever available).

**Data mining:** Data redundancy often leads to model over fitting in multivariate analysis. Such redundancy may arise due to in-source fragmentation and adducts in mass spectrometry. Inter-feature correlation will be examined across samples to identify covariant features. In case, they appear within same retention time window, raw chromatograms will be analyzed to identify putative adducts or fragments. They will be excluded from further analysis. Principal component analysis (PCA) will be used to examine any segregation of lipidomic signature and their correlation with phenotypes of interest (PCOS and sub-features of PCOS). Supervised analysis (PLS-DA and OPLS-DA) will be used to identify features that could predict phenotypes of interest. Iterative 'leave-one-out' cross validation (number of iteration

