> 20% of the size of the nested cohort) will be used to validate the model. For univariate analysis non-parametric statistical test assuming unequal variance will be employed given the limited sample size. Unpaired Mann-Whitney 'U' test with Bonferroni correction for multiple testing will be used identify lipids (say, set 'A') that shows significant difference in abundance between controls and cases at a given time point. Paired Mann-Whitney test with Bonferroni correction will be used to identify lipids (say, set 'B') that shows significant change in abundance with disease onset in naive subjects. Molecules (say, set 'C') that shows similar pattern of change with time in all three groups, i.e., subjects that present PCOS at beginning, those that develop PCOS during the study and those who never develop PCOS, will be excluded from further analysis to identify putative biomarkers. Rest of the molecules that are common in both sets (A and B) and shows similar pattern of change associated with disease status will be tested as potential biomarkers related to PCOS. In addition, the correlation between lipidomic signatures and non-PCOS clinical or biochemical parameters (such as, body weight, BMI, WC, body fat, fasting glucose, insulin concentration, liver fibrosis score, etc) will be examined. Receiver operating characteristic (ROC) analysis will be performed to examine the sensitivity and specificity of these candidate biomarkers for PCOS diagnosis. In case, there are significant number of new cases of PCOS in both 2nd and 3rd year, cases up to 2nd year will be used to identify consensus lipidomic changes associated with PCOS as described above. Rest of the cases will be used to prospectively validate PCOS markers through ROC analysis. In addition, the ability of baseline abundance of such molecules to predict PCOS incidence at a later time point will be examined using ROC analysis. This would help to identify a multivariate signature that could help to predict PCOS risk in naive subjects.

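### Blood draws are standardised for fasting but cycle day is not recorded, so a cycle-dependent compound, most plausibly a steroid, can appear as a PCOS difference

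*Protocol*

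**What the plan says.** Protocol section 1.4, Sample collection, states that "Serum samples will be collected from subjects fasting overnight". The rest of that section covers aliquots, storage and dispatch to the laboratory. The Clinical assessment section lists body measurements, Fibroscan, family history and medication. No section ties a menstrual date or cycle day to the draw. The work plan places visits in three-month windows (months 1-3, 13-15 and 25-27), not at a point in the cycle.

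The same Clinical assessment section makes a case from any two of three features: hyperandrogenism, "ovulatory dysfunction (oligo-ovulation, anovulation) and PCOM (by USG"). The GC-MS part of the Lipidomic Analysis section includes steroids: "For steroids, samples will be derivatized using MSTFA containing 0.5% TMSI".

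The Data mining text defines three sets of compounds:
- **Set A:** an unpaired Mann-Whitney test with Bonferroni correction finds what "shows significant difference in abundance between controls and cases at a given time point".
- **Set B:** "Paired Mann-Whitney test with Bonferroni correction will be used to identify lipids" whose abundance "shows significant change in abundance with disease onset in naive subjects".
- **Set C:** what "shows similar pattern of change with time in all three groups" (PCOS at the start, PCOS during the study, never PCOS) is dropped.

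Candidates must be in both A and B and not in C. The plan also examines "the correlation between lipidomic signatures and non-PCOS clinical or biochemical parameters". Cycle phase is not among the parameters named, although that list is left open. PCA, PLS-DA and OPLS-DA run alongside the univariate tests, and ROC analysis follows.

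**The concern.** A woman who does not ovulate has no post-ovulatory phase. If draws fall on arbitrary cycle days, ovulating controls will be caught after ovulation more often than a case group that includes oligo- and anovulatory women. The imbalance comes from the case definition, so it does not average out as noise would. A compound that varies with the cycle but is otherwise unrelated to PCOS would then differ between cases and controls.

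The filters do not exclude such a compound in principle. It can enter set A through the imbalance. It can enter set B when a previously unaffected woman stops ovulating as she becomes a case. It need not be removed by set C, because it does not change alike in all three groups. Such a compound would largely restate a diagnostic feature already in use. The protocol faults earlier lipidomic studies for leaving confounders such as BMI and age uncontrolled (section 1.1.2), so this is a fair test by its own standard.

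The timing matters. An analysis plan can add a covariate or a subgroup later, but it cannot recover a cycle day that was never recorded.

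**Working it through.** **Inputs from the protocol.** There are 200 participants, any two of three features make a case, and Bonferroni correction applies to both tests. The protocol gives no phase effect, no split of cases by feature and no count of lipid features, so there is no planned figure to reproduce.

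**Assumptions.** 30 cases v 170 controls; 50% of draws from ovulating women are post-ovulatory; 500 features, so the Bonferroni level is 0.05/500 = 0.0001; a compound with no PCOS effect shifts by d = 0.5, 1 or 2 SD after ovulation.

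**Step 1, phase shares.** If a share *a* of cases never ovulates, their post-ovulatory share is 0.5 × (1 − a). With a = 0.8 this is 10%; with a = 0.5 it is 25%.

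**Step 2, spurious shift in set A.** The shift is (control share − case share) × d.
- 10% of cases post-ovulatory: 0.40 × d = 0.2, 0.4 and 0.8 SD.
- 25%: 0.25 × d = 0.125, 0.25 and 0.5 SD.

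**Step 3, set A alone (simulated Mann-Whitney test; nominal rate 0.01%).**

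| Cases post-ovulatory | d = 0.5 | d = 1 | d = 2 |
|---|---|---|---|
| 10% | about 0.1-0.2% | about 1.5% | about 13% |
| 25% | about 0.02% | about 0.1-0.3% | about 1-2% |

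With equal phase shares the rate returns to nominal, so the imbalance is the cause. The case count matters too. At 10% post-ovulatory and d = 2, 12 cases v 188 controls (6% of 200) gives about 0.5%, and 45 v 155 (22.5%) gives about 29%. Both percentages come from the protocol's table of Indian studies.

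**Step 4, the joint rule.** For set B, take women who become cases during follow-up (converters), whose post-ovulatory share falls from 50% to 10%. Assume a within-woman correlation of 0.5, a signed-rank test for the paired comparison, and independence of A and B.
- 10 converters: the smallest two-sided exact p is 2/2^10 = 0.002, above 0.0001, so set B cannot be entered. At 14 it is 2/2^14 = 0.00012; at 15 it is 2/2^15 = 0.00006. At least 15 converters are needed.
- 20 converters: probability of passing A and B is below 0.001%, 0.003% and 0.26% for d = 0.5, 1 and 2.
- 30 converters: below 0.001%, 0.013% and 1.1%.

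At 30 converters and d = 2, set B passes at about 1.1/13 = 8.5%. With the 45-case set A rate the joint figure would be about 0.29 × 0.085 = 2.5%, the top of the range examined.

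**Step 5, where the joint rule does not help.** Set A reported by itself has no such protection, and neither do PLS-DA and OPLS-DA. The diagnostic ROC analysis compares cases and controls with the same phase mix, so any cycle-dependent component in a candidate distorts its apparent accuracy.

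**The case against.** The strongest counter-argument is that the plan's own selection rule nearly removes the artefact. This largely stands. A reader who simulated set A at an uncorrected 0.05 would find false-positive rates of about 16%, 44% and 86% and might take them as the plan's error rates. They are not, because the Data mining text applies Bonferroni to both tests and requires agreement between them.

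A reader might also infer that any signature found could not be an early marker. The documents do not support that. A separate ROC analysis asks whether baseline abundance predicts later PCOS in unaffected women. Neither group meets the case definition at baseline, so the built-in imbalance is mostly absent. It is not wholly absent, since a woman may have ovulatory dysfunction as her single feature.

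Three further points stand:
- Hyperandrogenism with polycystic morphology makes a case without any ovulatory defect, and oligo-ovulatory women still ovulate sometimes. Both dilute the imbalance.
- No document gives a cycle effect on serum lipids. The concern is most plausible for steroids and should not be extended to the lipidome as a whole.
- Anovulation is part of the disease. Adjusting the main analysis for phase could remove real signal, and adjustment confined to regularly cycling women would not deal with the anovulatory cases.

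Section 18 calls the project exploratory, and validation in other cohorts is intended. That limits the consequences, but a new cohort sampled in the same way would reproduce a phase artefact. The objection that adjustment belongs in an analysis plan holds for the analysis but not for recording the date.

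**Conclusion.** The point holds as a moderate, inexpensive-to-correct design gap. The protocol fixes fasting but does not record where each woman is in her cycle, while its case definition makes a phase difference between cases and controls likely. The exposure lies in set A, the supervised models and the diagnostic ROC analysis. It is small for candidates that must pass both A and B, and smaller for baseline prediction than for diagnosis.

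The size cannot be established from the documents. In the 30 v 170 illustration, set A alone ranges from near nominal to about 13% per cycle-dependent compound. The joint rule gives about 1% or less with 20 to 30 converters and zero with 10. These figures depend on the assumed phase shares, phase effects, feature count and case count. They do not show that a planned signature would be spurious.

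**What to change.** **Sample collection (section 1.4).** Add that the date of the last menstrual period, and hence the cycle day, is recorded at every draw.

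**Data mining.** Leave the main analysis as planned and add one sensitivity analysis. Compare cases only with controls whose samples are not post-ovulatory, report which candidate compounds survive, and flag the others as possible phase markers. Survival should mean a difference in the same direction. With post-ovulatory controls removed, a pure phase marker shifts by (case share × d) the other way: 0.10 × d or 0.25 × d under the two assumed shares. Drawing regularly cycling women in the same phase each year is optional.

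**Cost.** One question per visit. In the sensitivity analysis only, about half the controls are lost under the assumed share: 0.5 × 170 = 85 remain. The effective size n1·n0/(n1 + n0) falls from 30 × 170/200 = 25.5 to 30 × 85/115 = 22.2, so standard errors grow by about √(25.5/22.2) − 1 = 7%. A borderline candidate can drop out for that reason alone, so it should be flagged, not discarded. Phase will remain loosely defined in women with irregular cycles.
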